### **Enrollment (Day 1)**

- a) Re-evaluate whether the subjects can enter the study according to the test and examination results during the screening period, referring to the inclusion and exclusion criteria;
- b) Subjects were enrolled and received medicines according to the random number table;

c) The investigator and the subject agree on the time of the next follow-up visit.

**Follow-up 1 ( equivalent to the end of the first month)**

- a) Ask and record adverse events that have occurred since enrollment;
- b) Ask the patient about the first menstrual condition (menstrual period, cycle, menstrual volume) and symptoms of irregular menstruation after taking the medicine and make a score;
- c) The investigator and the subject agree on the time of the next follow-up visit.

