- 2) Experimental group2(Zhenqi Buxue Oral Liquid and Progesterone Capsules): Zhenqi Buxue Oral Liquid was taken orally, 10 ml at a time, twice a day for 3 menstrual cycles + orally from the second half of menstrual cycle, Progesterone Capsules 200mg, once a day for 10 days for 3 menstrual cycles
- 3) Active Comparator group (Progesterone Capsules): Progesterone Capsules 200mg, qd\*10 days\*3 menstrual cycles, orally

- Treatment Period: 3 month.
- Outcomes Measurement:
  - 1) Primary Outcome: Menstrual improvement in women including cycle period, menstrual volume, number of days with bleeding or spotting, monthly rates of amenorrhea
  - 2) Secondary Outcome:
    - a) Sex hormone levels: mainly FSH, LH, E2 and AMH
    - b) AFC: Changes in AFC in pelvic ultrasonography
    - c) SF-36: The change of the MOS item short from health survey
  - 3) Safety Assessment: Adverse reactions, Hepatic Function, Renal Function, Blood Glucose, Breast Ultrasound

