## **C. TECHNICAL ROUTE**

### **Screening Period (Day -30~0)**

- a) The researcher explained the research situation and informed the subjects, and the subjects signed the informed consent;
- b) Evaluate whether subjects can enter the study according to the inclusion and exclusion criteria;
- c) Collect basic information, medical history (including menstrual history, pregnancy and birth history) and demographic data, conduct routine physical examination (heart rate, blood pressure, height, weight); and irregular menstrual symptoms and scoring
- d) On the 2nd to 3rd day of the menstrual cycle (basic day), draw venous blood to check FSH, LH, E2, prolactin (PRL), testosterone (T), and AMH;
- e) Liver and kidney function;
- f) Pelvic ultrasound: on the 1st to 3rd day after menstruation is clean, after disinfection of the vulva, transvaginal ultrasound is performed to count bilateral ovarian AFC, breast ultrasound;
- g) The investigator and the subject agree on the time of the next follow-up visit.

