**Follow-up 2 (After taking the medicine in the second month, follow-up by WeChat or telephone)**

- a) Ask and record adverse events that have occurred since enrollment;
- b) Ask the patient about the second menstrual condition (menstrual period, cycle, menstrual volume) and the symptoms of irregular menstruation after taking the medicine and make a score;
- c) The investigator and the subject agree on the time of the next follow-up visit.

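### Cycle period has no defined start, so the first on-treatment cycle, read onset to onset, includes pre-dose days that dilute the treatment effect

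*Combined protocol and SAP*

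**What the plan says.** Section B defines the primary outcome as "Menstrual improvement in women including cycle period, menstrual volume, number of days with bleeding or spotting, monthly rates of amenorrhea". It gives no start or end point for a cycle, and no rule on which cycles count or how they are combined.

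Section C sets the timing:
- Screening is headed "Screening Period (Day -30~0". It includes the instruction "On the 2nd to 3rd day of the menstrual cycle (basic day), draw venous blood" and an ultrasound shortly after that menses ends.
- On Day 1, eligibility is re-checked against the screening results and medicine is handed out. No day of the menstrual cycle is specified.
- Follow-up 1 is "equivalent to the end of the first month" and has the investigator "Ask the patient about the first menstrual condition (menstrual period, cycle, menstrual volume", meaning the first menstruation after starting medicine.
- Follow-up 2 has the investigator "Ask the patient about the second menstrual condition (menstrual period, cycle, menstrual volume". Follow-up 3 asks about current menstruation without itemising cycle.

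Section D plans an unpaired t-test or chi-square test, with no baseline adjustment. Section A and the inclusion criteria in Section B indicate that women with absent as well as infrequent menses are intended.

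**The concern.** A cycle is ordinarily counted from one onset to the next. On that reading, the cycle belonging to the first bleed after starting medicine runs back to the last bleed before Day 1, so part of it was over before treatment could act. Only Follow-ups 1 and 2 itemise cycle, so one of the two itemised recordings is affected. In women with infrequent menses followed for about three months, it may be the only completed cycle.

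At stake is whether the primary cycle measure shows the effect it is meant to show. Centres may also record it differently, because nothing fixes the start point.

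**Working it through.** The plan gives no expected cycle length, SD or effect, so there is no figure of its own to reproduce. The total of 330 comes without assumptions and does not bear on this point.

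**1. Does the first cycle straddle Day 1?** Taking a month as 30 days (assumption), a cycle lying wholly between Day 1 and Follow-up 1 needs two onsets in about 30 days, so it could last at most about 29 days. That is unlikely in women enrolled for infrequent menses. Day 1 also comes after the screening blood draw and post-menstrual ultrasound. The next onset could coincide with Day 1 only if the cycle were about 32 days or shorter.

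**2. Pre-dose share.** Let P be days from last onset to Day 1, and T days from Day 1 to first onset. The recorded cycle is C = P + T and the pre-dose share is P/(P+T). With T = 10, P = 5, 15, 28 and 90 give 33%, 60%, 74% and 90%.

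**3. Attenuation.** Assumptions: P uniform on 5–30 days (mean 17.5), usual cycle L with SD 6 days, 90 days of follow-up, and treatment multiplying time after Day 1 by 0.8. The true shortening is 0.2 × L; the straddling interval shows 0.2 × (L − 17.5). Simulation of 200,000 women per setting agrees and supplies the last two columns.

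| L (days) | True shortening | Straddling interval shows | Lost | Difference in woman-level mean of completed cycles | Lost |
|---|---|---|---|---|---|
| 35 | 7 | 3.5 | 50% | 5.9 | 16% |
| 45 | 9 | 5.5 | 39% | 7.5 | 17% |
| 60 | 12 | 8.5 | 29% | 10.0 | 17% |

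The straddling interval makes up about 32–40%, 44–53% and 60–93% of a woman's completed cycles at the three lengths (treated to untreated). At 60 days it is the only completed cycle in about 86% of untreated and 19% of treated women.

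**4. Long absence.** A woman with P = 90 and T = 10 is recorded at 100 days; one with P = 5 and T = 30 is recorded at 35, although the first responded sooner. Now assume T has mean 25 and SD 8 days, independent of P, and some women have P of 90–180 days. Those among them whose T is in the fastest quartile fall in the longest quartile of C 100% of the time if such women are 10% of the sample, and 72% if they are 30%.

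**5. Precision in that second model.** Power = Φ(Δ/(SD·√(2/n)) − 1.96), with Δ = 4 days and n = 110 per arm (330/3; equal allocation is assumed):
- T alone, SD 8.0: 96%
- C with no long-absence women, SD 10.8: 79%
- C with 10% long-absence women, SD 37.6: 12%
- C with 30%, SD 56.7: 7.5%

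Because C = P + T, adjusting C for P leaves the SD of T and returns power to 96%.

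**6. Candidate analyses in the step 3 model** (effect divided by SD):

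| Analysis | L = 35 | L = 45 | L = 60 |
|---|---|---|---|
| Straddling interval, unadjusted | 0.66 | 1.00 | 1.54 |
| Days from Day 1, unadjusted | 0.44 | 0.65 | 1.00 |
| Woman-level mean, all completed cycles | 1.78 | 1.92 | 2.02 |
| Woman-level mean, only cycles starting after Day 1 | 1.64 | 1.68 | 1.57 |

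Adjusted for P, the first two rows become the same analysis, with a small gain over the unadjusted straddling interval (0.66 to about 0.67 at 35 days). In the last row at 60 days, only 13% of untreated but 81% of treated women have such a cycle, and the apparent shortening is 7.6 of 12 days.

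**The case against.** The documents do not say that cycle runs back to the last pre-dose bleed, or that the first cycle enters the primary analysis. That is correct. The onset-to-onset reading is an inference, though the ordinary one, and the gap is itself a reason to define the term.

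A reader might infer that a woman with a quick return of menses is scored among the worst. The documents do not support this. The score at Follow-up 1 is unspecified, no direction or threshold is given for cycle length, and the same woman counts favourably on the monthly amenorrhea rate, another primary component. What can be said is that her recorded cycle is among the longest. Even that needs women with long absence to pass a screening that, read literally, requires a recent bleed. If that requirement is enforced, P is at most about 30 days and the extreme reversal does not arise, but the attenuation remains.

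A reader might also infer that the straddling interval is always noisier. It is not. In the step 3 model its SD in untreated women is 5.7–6.0 days against 6.0 for a full cycle, because P and T are parts of the same cycle. Precision is lost when long-absence women enter, or when P and T are unrelated as in step 5.

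Finally, P is fixed before randomisation and the second recorded interval starts after dosing, so no bias toward one arm follows. This stands.

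**Conclusion.** The concern holds in limited form. A primary component has no start point, and under its ordinary meaning the first recorded cycle nearly always includes time that treatment could not affect. In the assumed settings that interval hides 29–50% of the true shortening, and the woman-level mean loses about 16–17%. If long-absence women enter, precision on an unadjusted first cycle could fall sharply and individual responders would be misclassified.

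Cycle lengths, SDs, the distribution of elapsed time, the 20% and 4-day effects, 110 per arm and the 30-day month are all assumptions; none comes from the documents. The direction of the attenuation depends only on the onset-to-onset reading and on treatment acting after Day 1.

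**What to change.** - **Section C, Screening and follow-up visits:** record the onset date of the last bleed before Day 1 and the date of each later onset.
- **Section D:** analyse the first interval as days from Day 1 to first onset, adjusted for days from last bleed to Day 1, in place of an unadjusted t-test on the straddling cycle. State how a woman with no onset by month 3 is handled, for example as censored at that visit. Adjustment does not enlarge the difference in days; it puts the effect on time that treatment can change and removes the noise from elapsed time.
- **Supporting summary:** report the number of onsets from Day 1 to month 3 for every woman, including those with none or one.
- **Main analysis:** do not restrict cycle period to intervals starting after Day 1. Having such an interval depends on treatment.
- **Sections A, B and C:** reconcile the bleed required at screening with the intended inclusion of women with amenorrhea.

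The cost is slightly more date collection and a covariate-adjusted model. The last-bleed date should come from the menstrual history already taken. Later onsets can come from the visits and the diary card, whose contents the plan does not describe and which may need a date field.

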## B. STUDY METHOD AND DESIGN

- 330 women with menstrual disorders were observed in a prospective multi-center randomized controlled clinical trial.
- Inclusion Criteria:
  - 1) Aged between 25 and 40 years old;
  - 2) Patients with oligomenorrhea or oligomenorrhea or menopause within three months (see Appendix 1: Diagnostic Criteria of Traditional Chinese and Western Medicine)
  - 3) Meet the clinical medication conditions for progesterone to regulate menstruation
  - 4) The research subjects were informed and voluntarily participated in this study, and signed the informed consent at the same time.
- Exclusion Criteria:
  - 1) Age <25 years or >40 years old, pregnant or breastfeeding women
  - 2) Ovarian dysfunction caused by local ovarian surgery, radiotherapy and

chemotherapy for previous malignant tumors, taking hormones or immunosuppressive drugs;

- 3) Combined with serious or unstable physical diseases that may affect the efficacy of drugs and the conduct of trials, including liver, kidney, gastrointestinal, cardiovascular, respiratory, endocrine, neurological, immune or blood system diseases, etc., mental patients .
- 4) Those who were allergic to the drugs used in the trial or had serious adverse reactions in the past;
- 5) Breast cancer or family history of breast cancer in first-degree relatives, irregular vaginal bleeding, uterine fibroids ( $\geq 3$ cm), endometriosis, atypical endometrial hyperplasia, endometrial cancer and other hormone-dependent reproduction Systemic diseases and other malignant tumors;
- 6) Those with a history of thromboembolic disease or thrombosis;
- 7) Participated in a clinical trial of another research drug within 3 months prior to inclusion in this study (the first interview);
- 8) Those who have used related drugs in the past 3 months or have abused or depended on substances (alcohol or drugs) in the past 3 months; heavy smokers (smokers who smoke 20 or more cigarettes per day);
- 9) Those who met the inclusion criteria, did not follow the doctor's advice, were unable to judge the curative effect or were unable to evaluate the curative effect due to incomplete data.

➤ Methods: The participants were divided randomly into 3 groups:

- 1) Experimental group1(Zhenqi Buxue Oral Liquid): Zhenqi Buxue Oral Liquid, 10 ml each time, 2 times a day for 3 menstrual cycles, orally

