**Follow-up 3 (the third month after taking the medicine, equivalent to the end of the third month)**

- a) Ask and record adverse events that have occurred since enrollment;
- b) perform routine physical examinations (heart rate, blood pressure, weight);
- c) Ask the patient about the current menstruation and irregular menstruation symptoms, (or pregnancy), perform symptom scores, and evaluate the effectiveness of the drug;
- d) FSH, LH, E2, PRL, T, AMH (blood draw on day 2-3 of menstruation);
- e) Liver and kidney function;
- f) Pelvic ultrasound (bilateral ovarian AFC) examination, breast ultrasound;
- g) Subject returns untaken medication and checks (including used medication packaging) and filled diary card.

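### Follow-ups 1 to 3 list no item on outside hormones or menstrual-regulating products, and exclusion 9 as written could remove women after randomisation; a cheap improvement of low severity.

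*Combined protocol and SAP*

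**What the plan says.** Section C of the combined protocol and SAP itemises each visit. At Follow-up 1 staff record adverse events, "Ask the patient about the first menstrual condition (menstrual period, cycle, menstrual volume) and symptoms of irregular menstruation after taking the medicine", score the symptoms, and arrange the next visit. Follow-up 2, by WeChat or telephone, repeats these items ("Ask the patient about the second menstrual condition"). Follow-up 3 adds a physical examination, a hormone panel (FSH, LH, E2, PRL, T, AMH), liver and kidney function, and ultrasound. Its one medication item is "Subject returns untaken medication and checks (including used medication packaging) and filled diary card". What the diary card asks is not described.

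The rules on other drugs are in the exclusion criteria of section B. Exclusion 8 bars "Those who have used related drugs in the past 3 months". Exclusion 2 mentions "taking hormones or immunosuppressive drugs", which can be read as one cause of ovarian dysfunction or as a bar in its own right. Eligibility is last checked on Day 1: "Re-evaluate whether the subjects can enter the study according to the test and examination results during the screening period". Exclusion 9 lists women who met the inclusion criteria but "did not follow the doctor's advice", or whose response could not be judged, including because data were incomplete.

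Inclusion 3 requires every woman to "Meet the clinical medication conditions for progesterone to regulate menstruation". Group 1 is assigned the oral liquid alone; groups 2 and 3 receive progesterone capsules. The primary outcome is menstrual: cycle, volume, bleeding days and monthly amenorrhoea. Section D names t-tests and chi-square tests, defines no analysis population, and does not mention other medicines.

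**The concern.** Every woman in group 1 is a candidate for progesterone, none is assigned it, and the outcome is the bleeding that progesterone is given to regulate. No blinding is described, and a liquid is easily told from capsules. A group 1 woman whose menses do not return could therefore seek a progestogen elsewhere. The resulting bleed would count as improvement on the oral liquid and make it look closer to progesterone than it is. Bias in the other direction is also possible, for example if a woman in group 3 took an effective herbal product. Use that was never recorded is hard to recover afterwards.

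Exclusion 9 adds a second problem. If it were the route for dealing with such women, it would take them out after randomisation because of behaviour that may depend on the assigned treatment and on how well it worked. The women who remained would no longer be the groups that were randomised.

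**Working it through.** The plan gives no figure on this point, so there is none to reproduce. The check is mainly one of text.

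**1. Is outside use asked about?** Follow-up 1: adverse events, menstrual condition with symptom score, next visit. Follow-up 2: the same. Follow-up 3: adverse events, examination, menstrual condition with score, hormones, liver and kidney function, ultrasound, and return of trial medication, packaging and diary card. No listed item concerns other medicines. Returned packaging shows what trial drug was taken, not what else was. The hormone panel does not list progesterone, and its one on-treatment draw is on menstrual day 2-3 at Follow-up 3, so it is no substitute. The outcome list, section D and section E do not fill the gap. The diary card might.

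**2. Do the eligibility rules cover the treatment period?** Exclusion 8 looks back 3 months from entry. Exclusion 2, on either reading, is applied at entry. Both are last applied on Day 1. No section prohibits outside hormones during the three treatment cycles or defines rescue use.

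**3. When can exclusion 9 apply?** On Day 1 no trial treatment has been taken, so there is no treatment effect to judge and no trial regimen to have departed from. Exclusion 9 therefore describes events after entry, and using it means removing women already randomised.

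**4. What would outside progestogen in group 1 do?** Inputs, all assumed because the documents give none:

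- p1 and p3: the true monthly amenorrhoea rates in groups 1 and 3.
- u: the share of group 1 using outside progestogen, spread across the group.
- Users take on the group 3 rate.

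Then

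observed group 1 rate = p1 + u(p3 − p1)

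observed gap = p1 + u(p3 − p1) − p3 = (1 − u)(p1 − p3).

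The gap shrinks by the fraction u, whatever the true rates. For an assumed gap of 20 points (40% v 20%):

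| u | Observed gap |
|---|---|
| 5% | 0.95 × 20 = 19 points |
| 10% | 0.90 × 20 = 18 points |
| 20% | 0.80 × 20 = 16 points |

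The result depends on who the users are. If only women who would otherwise not bleed took outside progestogen, the group 1 rate would fall by u(1 − p3). At 5% use and p3 = 20% that is 0.05 × 0.80 = 4 points, leaving 16. The documents support neither pattern over the other, so these figures show how the mechanism works and are not an estimate of bias.

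**The case against.** The visit lists are a short outline, not a case report form, so silence in them is weak evidence. A patient-completed diary card exists and is a natural place to record other medicines. Treatment lasts only three cycles, recent users of related drugs are kept out at entry, and nothing in the documents suggests that outside use would be frequent. With 5% to 10% use spread across group 1, the gap shrinks by only 5% to 10% of itself. Exclusion 9 also gives the plan some route, though a crude one, for handling such women.

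Most of this stands, and it limits the point. A reader might infer that outside use will go unrecorded, or that the group 1 result will be biased. The documents support neither: they leave recording unspecified and say nothing on how often use would occur. A reader might also infer a definite loss of power. That would need response rates, a rate of use and an allocation ratio, and none of these is given.

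Two things survive. If the card has no such field, the trial could not later show that use was rare. And exclusion 9 is a poor remedy, because it acts by removing randomised women.

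**Conclusion.** The point holds as a low-severity improvement. The follow-up visits list no item on outside hormones or menstrual-regulating products, and the diary card's content is unknown. If use occurs and is not captured, it cannot be reported or allowed for. Outside progestogen in group 1 would then narrow the group 1 v group 3 difference by roughly the share of users. That proportion assumes use spread across the group and users reaching the group 3 rate; more selective use would narrow it further. The actual size is unknown and is small unless use is common. Exclusion 9, applied as written, would remove non-adherent or unevaluable women after randomisation and could bias any between-group comparison; the documents give no basis for putting a number on this.

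**What to change.** 1. At Follow-ups 1, 2 and 3, or on the diary card, record with dates any non-trial sex hormones, ovulation-inducing drugs, and herbal or proprietary products taken to regulate menses. If the diary card already does this, say so in the protocol.
2. State that all randomised women stay in their assigned group for the primary comparison, and that exclusion 9 is not used to remove anyone after randomisation.
3. Report outside use by group.

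A sensitivity analysis that recodes bleeds after outside progestogen in group 1 alone is not recommended. It could only worsen group 1's result, would need a time window that nothing in the documents supplies, and would leave outside use in the other groups untouched.

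The cost is one extra question or field per visit, one sentence on exclusion 9 and one descriptive table. Entry screening, the visit schedule and the sample size do not change. If the field already exists, only items 2 and 3 and a line of confirmation are new.

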**Follow-up 2 (After taking the medicine in the second month, follow-up by WeChat or telephone)**

- a) Ask and record adverse events that have occurred since enrollment;
- b) Ask the patient about the second menstrual condition (menstrual period, cycle, menstrual volume) and the symptoms of irregular menstruation after taking the medicine and make a score;
- c) The investigator and the subject agree on the time of the next follow-up visit.

**Follow-up 3 (the third month after taking the medicine, equivalent to the end of the third month)**

- a) Ask and record adverse events that have occurred since enrollment;
- b) perform routine physical examinations (heart rate, blood pressure, weight);
- c) Ask the patient about the current menstruation and irregular menstruation symptoms, (or pregnancy), perform symptom scores, and evaluate the effectiveness of the drug;
- d) FSH, LH, E2, PRL, T, AMH (blood draw on day 2-3 of menstruation);
- e) Liver and kidney function;
- f) Pelvic ultrasound (bilateral ovarian AFC) examination, breast ultrasound;
- g) Subject returns untaken medication and checks (including used medication packaging) and filled diary card.

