**D. STATISTICS ANALYSIS**

Data was analyzed using SPSS Version 25. All quantitative information are expressed as mean values  $\pm$  standard deviation (SD). Statistical significance was assessed using unpaired Student's t-test or chi-square test. Probability values of less than 0.05 were considered significant and an asterisk identifies such significance in the figures. We will also compare the adverse effect of each group using descriptive statistics.

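### Liver and kidney function is tested once after baseline and the plan offers only group means and SDs, so a few large individual rises could go unreported

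*Combined protocol and SAP*

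**What the plan says.** Section B lists the safety outcomes: "Safety Assessment: Adverse reactions, Hepatic Function, Renal Function, Blood Glucose, Breast Ultrasound". It gives no threshold, grade or definition of an abnormal result for any of them.

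In Section C, liver and kidney function and breast ultrasound appear in the Screening Period and again at Follow-up 3 ("Liver and kidney function"). Follow-up 1 lists adverse-event questions, menstrual history, a symptom score and the next appointment. Follow-up 2 has the same content and is held remotely ("After taking the medicine in the second month, follow-up by WeChat or telephone"). Neither lists a laboratory test. No visit or test is described for a woman who stops treatment early.

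All three follow-ups include the instruction "Ask and record adverse events that have occurred since enrollment". Follow-ups 1 and 2 end by agreeing the next contact. Follow-up 3 does not, and no later contact is listed.

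Section D is the whole analysis plan. On summaries it says "All quantitative information are expressed as mean values" with SD. It names the unpaired t-test and the chi-square test, a 0.05 threshold, and a descriptive comparison of adverse effects by group. It has no shift table, threshold count or individual listing, and no rule on when an abnormal laboratory value counts as an adverse event.

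**The concern.** Drug-related liver or kidney injury usually shows as a large change in a few women, not a small shift in everyone. A group mean responds weakly to such a pattern. The outliers also inflate the SD, which enlarges the standard error of the t-test and works against detecting the difference they cause.

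The plan rests on a single post-baseline value per woman, and the only summary it states for that value is the one least suited to showing individual abnormality. The object of the study includes clarifying the safety of the oral liquid. As written, the report could state that liver function did not differ between groups while several women in one arm had values at several times the upper limit. Someone would have to choose to record those values as adverse events for them to appear at all.

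A second, smaller gap concerns the denominator. A woman who stops in month 1 or 2 has no test tied to her stopping. Her only scheduled test is at month 3, and the plan does not say how a missing test is to be reported.

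**Working it through.** The plan states no safety rate, SD or power, so there is no figure of its own to reproduce. What follows is an illustration.

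**Inputs from the documents.** "330 women with menstrual disorders were observed in a prospective multi-center randomized controlled clinical trial"; "The participants were divided randomly into 3 groups"; "Treatment Period: 3 month"; significance at p<0.05.

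**Assumptions.** Equal allocation (the ratio is not stated), so 330/3 = 110 per arm; ALT mean 20 U/L, SD 8 U/L, upper limit 40 U/L; two-sided test; k women in one arm at 200 U/L (five times the limit) and none in the other.

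**Step 1: the arm mean.** Mean = (k × 200 + (110 − k) × 20)/110. For k = 3: (600 + 2140)/110 = 24.9 U/L, well below 40.

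**Step 2: the arm SD.** Sum of squares = (109 − k) × 8² + k × (200 − mean)² + (110 − k) × (20 − mean)². For k = 3 this is about 101,333, so SD = √(101,333/109) = 30.5.

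**Step 3: the t-test at expected values.** SE = √(30.5²/110 + 8²/110) = 3.01; t = 4.91/3.01 = 1.63; p = 0.10 on 218 degrees of freedom.

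| Women at 200 U/L (of 110) | Arm mean | Arm SD | p |
|---|---|---|---|
| 1 | 21.6 | 18.9 | 0.40 |
| 2 | 23.3 | 25.4 | 0.20 |
| 3 | 24.9 | 30.5 | 0.10 |
| 5 | 28.2 | 38.5 | 0.03 |

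With three women affected, changing the peak to 120 or 400 U/L gives p = 0.15 or 0.09. The conclusion does not depend on the exact height of the rise.

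**Step 4: simulation.** Draw both arms from Normal(20, 8), set k values in one arm to 200, and apply the t-test. The share of trials with p<0.05 is about 5-6% for k = 2, 17-18% for k = 3 and 43-44% for k = 4. Repeating k = 3 with the SD set to 6 or 12 (20,000 trials each) gives about 15% and 19%.

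**Step 5: the same data as a count.** 3/110 = 2.7%, exact (Clopper-Pearson) 95% CI 0.57% to 7.76%, against 0/110. Fisher's exact test gives p = 0.25 and the uncorrected chi-square p = 0.08. Fisher's test needs 6 against 0 before p<0.05 (5 against 0 gives 0.06).

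**Step 6: missing tests.** If no abnormal value is seen among n tested women, the one-sided 95% upper bound on the rate is 1 − 0.05^(1/n). This is 2.7% for n = 110, 3.0% for 99, 3.3% for 88 and 3.8% for 77, that is, with 0, 10, 20 or 30% untested (assumed). This shows the loss of precision only. Any bias from untested women being different cannot be sized from the documents.

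**The case against.** The strongest reply is that the plan has other routes to an injury. Adverse events are asked about at each of the three follow-ups and compared by group, and a chi-square test is named, so categorical analysis is not excluded. That stands for a symptomatic or clinically recognised injury. It does not cover a symptomless rise, because no rule turns a laboratory value into an adverse event.

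A second reply is that a table reading 25 ± 30 against 20 ± 8 would alert a careful reader. It would, but it would not say how many women were affected or how severely.

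A third is that the low t-test rate does not show counts to be better at reaching significance. That is right: with 3 against 0, Fisher's p is 0.25. The case for counts is that they display the abnormality, not that they have more power.

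A reader might infer several stronger points that the documents do not support:

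- **That final results come back after the last contact.** No laboratory turnaround is stated, and Follow-up 3 may span several days, since hormone blood is tied to menstrual days 2-3. The text shows only that no later contact is listed and that no handling of an abnormal final result is described.
- **That the safety data come only from women who tolerated treatment.** No safety set is defined, and nothing says that a woman who stops must miss Follow-up 3.
- **That breast findings are averaged too.** Breast ultrasound is not clearly quantitative, so the mean-and-SD sentence need not govern it.

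Finally, one end-of-treatment test over three months is a design choice. This point does not ask for an interim test.

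**Conclusion.** The concern holds as a reporting gap. Liver and kidney function has one post-baseline measurement, and the only stated summary for quantitative data is mean and SD, with no per-woman count of abnormal values. Large rises in a few women can be hidden, though they need not be.

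Under the assumptions above, three of 110 women at five times the limit leave the arm mean near 25 U/L, and a significant t-test appears in only about one trial in six. The size rests on assumed ALT figures and equal allocation. The direction holds across the ranges tried: peak 120 to 400 U/L and SD 6 to 12. Two smaller gaps also stand: nothing is said about reporting early stoppers without a post-baseline test, or about recording an abnormal Follow-up 3 result. Safety reporting is affected; the primary outcome is not. The sponsor should make the change, but the trial's design does not depend on it.

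**What to change.** Add to Section D:

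1. Report liver and kidney results per woman by arm, as a shift table from screening to the post-baseline value and as the number and percentage above preset multiples of the laboratory upper limit, with exact 95% CIs. Set the multiples before the data are seen. Keep means and SDs as a supplement, and present the counts as descriptive.
2. Report breast ultrasound as the number of women in each arm with new or worsened findings.
3. Report by arm how many women stopped treatment early and how many of those have no post-baseline liver and kidney test. Give the number tested as the denominator for every safety count.
4. State how an abnormal Follow-up 3 result is recorded, including whether and when it counts as an adverse event, since no later contact is listed.

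Items 1 to 3 are analysis wording applied to data already collected or to visit records. Item 4 is a recording rule. None of them adds a visit, a test or a participant.
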